8.2 Secondary Endpoints

The secondary efficacy endpoints in this study are:

- For Ex-US submission only: Hb maintenance: Mean change from baseline (CFB) in Hb averaged over 8 weeks of treatment at Weeks 28 to 36, without rescue therapy within 6 weeks prior to and during this 8-week evaluation period.
- Mean CFB in LDL cholesterol averaged over Weeks 12 to 28
- Mean CFB in the SF-36 PF subscore averaged over Weeks 12 to 28 in the Intent to Treat (ITT) subjects with baseline PF subscore below 35
- Mean CFB in SF-36 Vitality subscore averaged over Weeks 12 to 28 in ITT subjects with baseline vitality subscore below 50
- Blood pressure effect
 - a. Mean CFB in mean arterial pressure (MAP) averaged over Weeks 20 to 28, measured as the mean of the triplicate measurements 5 minutes apart
 - b. Time to (and proportion of subjects with) worsened hypertension (defined as systolic BP > 170 mmHg or diastolic BP > 110 mmHg measured, and an increase from baseline of ≥ 20 mmHg [systolic BP] or ≥ 15 mmHg [diastolic BP], confirmed by the mean of triplicate measurements 5 minutes apart)
- Time to (and proportion of subjects who received) rescue therapy (composite of RBC transfusion, ESA use, and IV iron) in the first 24 weeks of treatment
- Time to (and proportion of subjects who received) rescue therapy (composite of RBC transfusion, ESA use, and IV iron) in the first 52 weeks of treatment

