3 STUDY DESIGN

This is a Phase 3, multi-center, randomized, double-blind, placebo-controlled study in anemic subjects with Stage 3, 4, or 5 CKD who are not on dialysis.

This study will consist of three study periods:

- **Screening Period:** Up to 6 weeks
- **Treatment Period:** Variable for individual subjects. In order to complete the Treatment Period simultaneously for all study subjects, the minimum treatment duration may be less than 52 weeks, with a maximum treatment duration of up to 3 years after the last subject is randomized.
- **Post-Treatment Follow-Up Period:** 4 weeks

3.1 IN ORIGINAL PROTOCOL AND AMENDMENT 1

Following the Screening Period, subjects are randomized to 1 of 6 treatment arms, defined by their dose frequency during maintenance (see Table 1). The randomization will result in a 2:2:2:1:1:1 ratio of subjects receiving roxadustat or placebo, respectively.

Randomization stratification factors include screening Hb values, cardiac/cerebrovascular/thromboembolic medical history, and estimated glomerular filtration rate (eGFR), and geographic region.

The Investigator, study site staff, subject, and the sponsor, are blinded to study drug, but not to dose or dosing frequency. Additionally, all efforts will be made to keep subjects blinded to study Hb values.

Study drug will be dosed TIW for anemia correction until subjects achieve a Hb value of ≥ 11 g/dL and ≥ 1 g/dL increase from baseline at two consecutive visits. Once these criteria are met, a dose frequency conversion to QW or BIW or a continuation of TIW will occur according to the subject's assigned treatment arm at randomization, defining entry into the maintenance phase.

Table 1. Study Drug Dose Frequencies

Treatment Arms	Correction	Maintenance	n (Roxadustat)	n (Placebo)
1A	TIW	QW	100*	0
1P	TIW	QW	0	50*
2A	TIW	BIW	100	0
2P	TIW	BIW	0	50
3A	TIW	TIW	100	0
3P	TIW	TIW	0	50

A=Active, P= Placebo

*These numbers are based on a sample size of 450 and would increase if overall sample size increases.

3.2 UNDER AMENDMENT 2 & 3

Following the Screening Period, subjects will be randomized in a 2:1 ratio to receive roxadustat (approximately 300-800 subjects) or placebo (approximately 150- 400 subjects). Randomization is stratified by the following factors:

- Screening Hb values (≤ 8 g/dL vs > 8 g/dL)
- History of cardiovascular, cerebrovascular or thromboembolic diseases (Yes vs No)
- eGFR (< 30 mL/min/1.73 m² vs ≥ 30 mL/min/1.73 m²)
- Geographic region (US vs Ex-US).

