4.2 SECONDARY ENDPOINTS

The secondary efficacy endpoints in this study are:

- For Ex-US submission only: Hb maintenance: Mean change from baseline (CFB) in Hb averaged over 8 weeks of treatment at Weeks 28 to 36, without rescue therapy within 6 weeks prior to and during this 8-week evaluation period.
- Mean CFB in Hb during the evaluation period (defined as Week 28 until Week 52) in subjects with baseline CRP > ULN
- Proportion (%) of subjects with Hb Level ≥ 10 g/dL between Week 28 to 36, without use of rescue therapy within 6 weeks prior to and during these 8-week evaluation periods.
- Hb maintenance by dose frequency: TIW, BIW, QW
- Mean CFB in LDL cholesterol averaged over Weeks 12 to 28
- Time to (and proportion of subjects who received) rescue therapy (composite of blood/RBC transfusion, ESA use, and IV iron) in the first 52 weeks of treatment
- Mean CFB in SF-36 Vitality subscore averaged over Weeks 12 to 28
- Progression of CKD: rate of change in eGFR over time adjusted by baseline eGFR, censored at dialysis or kidney transplant
- Time to (and proportion of subjects who received) blood/RBC transfusion in the first 52 weeks of treatment
- Mean CFB in the SF-36 PF subscore averaged over Weeks 12 to 28
- Blood pressure effect
 - a. Mean CFB in mean arterial pressure (MAP) averaged over Weeks 20 to 28, measured as the mean of the triplicate measurements 5 minutes apart
 - b. Time to (and proportion of subjects with) worsened hypertension (defined as systolic BP ≥ 170 mmHg and an increase from baseline of ≥ 20 mmHg, OR diastolic BP ≥ 110 mmHg and an increase from baseline of ≥ 15 mmHg, confirmed by the mean of triplicate measurements 5 minutes apart)

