6. Time to rescue therapy (composite of blood/RBC transfusion, ESA use, and IV iron) in the first 52 weeks of treatment will be compared using Inverse Probability of Censoring Weighted (IPCW) model detailed in Appendix A or Cox Proportional Hazards model as deemed appropriate. The Cox regression model will adjust for baseline Hb, baseline eGFR and other randomization stratification factors. Hazard ratio and its associated 95% CI will be computed between the roxadustat group versus pooled placebo. Superiority will be declared if the upper bound of the 2-sided 95% CI of the hazard ratio does not exceed one. Proportion of subjects who received rescue therapy over the treatment period will be derived using Kaplan-Meier approach.
7. Mean CFB in the SF-36 Vitality subscore averaged over Weeks 12 to 28 for the two treatment groups will be compared using an MMRM model as outlined above. A subgroup of subjects with baseline vitality subscore below 50 will be analyzed as a sensitivity analysis.
8. Progression of CKD measured by rate of change in eGFR over time adjusted by baseline eGFR, censored at chronic dialysis or kidney transplant will be analyzed using random slope and intercept model. Annualized eGFR slope over time is estimated by a random slope and intercept model using all available eGFR values (one baseline and all post-treatment values up to End of Treatment Period or start of chronic dialysis or kidney transplant) adjusted by Baseline Hb, Region, CV history at Baseline and the interaction terms Baseline eGFR by time point and Baseline Hb by time point). All assessments collected after initiation of chronic dialysis or kidney transplant will be excluded from the analysis.
9. Time to blood/RBC transfusion in the first 52 weeks of treatment will be compared using Inverse Probability of Censoring Weighted (IPCW) model detailed in Appendix A or Cox Proportional Hazards model as deemed appropriate. The Cox regression model will adjust for baseline Hb, baseline eGFR and other randomization stratification factors. Hazard ratio and its associated 95% CI will be computed between the roxadustat group versus pooled placebo. Superiority will be declared if the upper bound of the 2-sided 95% CI of the hazard ratio does not exceed one. Proportion of subjects who received blood/RBC transfusion over the treatment period will be derived using Kaplan-Meier approach.

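### SAP 12.3 items 6 and 9 derive the rescue and transfusion proportions over the whole treatment period, although SAP 4.2 defines both endpoints over the first 52 weeks

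*SAP*

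**What the plan says.** **Endpoint definitions.** SAP 4.2 lists, as time to event and as proportion of subjects, "rescue therapy (composite of blood/RBC transfusion, ESA use, and IV iron) in the first 52 weeks of treatment". It lists transfusion in the same form: "Time to (and proportion of subjects who received) blood/RBC transfusion in the first 52 weeks of treatment". Protocol 8.2 sets the same window for the composite, "rescue therapy (composite of RBC transfusion, ESA use, and IV iron) in the first 52 weeks of treatment", next to a 24-week version. The protocol does not set that window for transfusion alone. Protocol 8.3 lists RBC transfusion as an additional evaluation with no time limit.

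**Analysis text.** In SAP 12.3 item 6, time to rescue "in the first 52 weeks of treatment will be compared using Inverse Probability of Censoring Weighted (IPCW) model" or by a Cox model. Superiority is judged on the confidence limit of the hazard ratio. The item then adds: "Proportion of subjects who received rescue therapy over the treatment period will be derived using Kaplan-Meier approach". Item 9 has the same structure and ends: "Proportion of subjects who received blood/RBC transfusion over the treatment period will be derived using Kaplan-Meier approach".

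**Length of treatment.** SAP 3 makes the treatment period variable. It may be shorter than 52 weeks for some subjects, "with a maximum treatment duration of up to 3 years after the last subject is randomized".

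**The concern.** Each endpoint has two halves, a time to event and a proportion, and both halves are defined over 52 weeks. The analysis text keeps that window for the time to event and drops it for the proportion. A programmer who followed items 6 and 9 literally would put a percentage covering one period beside a hazard ratio covering another.

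A Kaplan-Meier proportion over a period of varying length also has no time point of its own. If it is taken where the curve ends, it rests on the subjects who enrolled earliest and stayed on treatment longest. Dropout matters most there. SAP 13.1.2 already suspects differential dropout between the arms, and SAP Appendix 8 offers inverse-probability weighting because informative censoring can bias conventional survival methods. Nothing in items 6 or 9 says that the Kaplan-Meier proportion is weighted.

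**Working it through.** The plan states no rate, event count or power for either endpoint, so there is no planned figure to reproduce. The check is a comparison of windows, followed by an illustration of size.

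**Step 1: windows side by side**

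| Quantity | Composite rescue | Blood/RBC transfusion |
|---|---|---|
| Protocol endpoint | 52 weeks (8.2) | no window (8.3, additional) |
| SAP 4.2 endpoint, time and proportion | 52 weeks | 52 weeks |
| SAP 12.3 model comparison | 52 weeks (item 6) | 52 weeks (item 9) |
| SAP 12.3 Kaplan-Meier proportion | treatment period (item 6) | treatment period (item 9) |
| SAP 4.3 time to, and proportion, over the treatment period | listed | not listed |

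**Step 2: does the SAP use the term treatment period to mean 52 weeks?** Three places bear on this.
- SAP 4.3 lists composite rescue over 24 weeks and over the treatment period as additional endpoints, apart from the 52-week secondary endpoint. ESA rescue and IV iron follow the same pattern.
- SAP 10.2, on dose adjustments, adds an explicit limit at Week 52 when it means the treatment period cut at that week. Items 6 and 9 carry no such limit on the proportion.
- The default reference period for efficacy time-to-event analyses (SAP 12, Efficacy Emergent Period) ends at the earlier of 7 days after last dose and the end-of-treatment visit. It has no cut at Week 52.

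No section says that the Kaplan-Meier estimate is to be read at Week 52.

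**Step 3: size, with assumed rates.** For a constant hazard h per year, the proportion with an event by t years is 1 − exp(−h × t). The hazards are assumptions.

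Central case, 0.4 (placebo) and 0.1 (roxadustat):
- 1 year: 1 − exp(−0.4) = 33% and 1 − exp(−0.1) = 10%, a difference of 23 points.
- 3 years: 1 − exp(−1.2) = 70% and 1 − exp(−0.3) = 26%, a difference of 44 points.
- Hazard ratio: 0.1 / 0.4 = 0.25 at both times.

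Range, placebo 0.2 to 0.6 and roxadustat 0.05 to 0.15:
- 1 year: 18–45% vs 5–14%.
- 3 years: 45–84% vs 14–36%.

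A second route starts from assumed 52-week proportions p, with weekly hazard −ln(1 − p)/52. For 30% vs 10%:

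| Week | Placebo | Roxadustat | Difference (points) |
|---|---|---|---|
| 52 | 30.0% | 10.0% | 20 |
| 104 | 51.0% | 19.0% | 32 |
| 156 | 65.7% | 27.1% | 39 |

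The hazard ratio is ln(0.9)/ln(0.7) = 0.295 throughout. In both illustrations the difference nearly doubles between one and three years while the hazard ratio stays the same.

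**The case against.** The strongest reply is that this is loose wording. Each item opens with the 52-week window, SAP 4.2 fixes the window for the proportion, and a Kaplan-Meier curve over a longer period still contains its Week 52 value. Table specifications sit in a separate document (SAP 1) that may settle the matter. Part of this stands: the SAP does not say that the last point of the curve will be reported, and the printed tables cannot be foreseen from here. It does not remove the conflict, because the SAP uses the longer period as a window in its own right and never names Week 52 as the reading point.

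Four stronger readings are tempting, and the documents do not support them.
- **The confirmatory result is at risk.** It is not. Both items compare time to event over 52 weeks, and superiority depends only on the hazard ratio. The proportion has no test and no place in the fixed sequence.
- **The protocol also defines transfusion over 52 weeks.** It does so only for composite rescue. The 52-week transfusion endpoint comes from the SAP.
- **SAP 4.3 already holds the whole-period version of both endpoints.** It does for rescue. For transfusion it has packs per patient-month and an exposure-adjusted incidence rate by component, but no time to event or proportion over the treatment period.
- **The illustrated percentages forecast this trial.** They do not. They show that cumulative incidence grows with the window, under hazards that are assumed and assumed constant.

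**Conclusion.** The mismatch is real, and it is confined to the proportion half of two secondary endpoints. As written, items 6 and 9 call for a quantity other than the one in SAP 4.2, without a fixed time point. For rescue, SAP 4.3 strengthens the case by listing the whole-period version as a separate endpoint. For transfusion, the case rests on SAP 4.2 against item 9, and on how the SAP uses the term elsewhere.

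What changes is the reported proportions and the difference between them. Under the central assumed hazards, the difference would be 44 points at three years instead of 23 at one year. The direction is certain for the proportions themselves, since cumulative incidence cannot fall with time. The amount depends on hazards, their constancy and numbers at risk, none of which the documents give. A correction is worthwhile because these percentages are likely to be quoted beside the hazard ratio, and because settling the time point before unblinding leaves no choice to be made afterwards.

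**What to change.** - In SAP 12.3 items 6 and 9, replace the treatment-period wording with: at Week 52, as the Kaplan-Meier estimate with 95% CI, from the same 52-week data as the hazard ratio.
- Keep the whole-period rescue proportion where it already is, among the additional endpoints of SAP 4.3.
- If a whole-period transfusion proportion is wanted, add it to SAP 4.3 as an additional endpoint, since there is no entry for it now.

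The cost is two sentences in the SAP, plus one optional line in 4.3, and a check that the table specifications agree. No new data, design change or change to the testing sequence is needed.

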5 GENERAL STATISTICAL CONSIDERATIONS

5.1 SAMPLE SIZE DETERMINATION

A total of at least 450 and up to 1200 planned subjects will be randomized in a 2:1 ratio to receive either roxadustat (at least 300, but at most 800 subjects) or placebo (at least 150, but at most 400 subjects) in a double-blind manner.

The study is sufficiently powered for both regionally-based primary efficacy endpoints. A minimum of 450 subjects are planned to be randomized to receive roxadustat or placebo (2:1 with approximately a minimum of 300 roxadustat vs 150 placebo) in a double-blind manner in order to support the primary endpoint(s) of the study.

For US (FDA) Submission Primary Efficacy Endpoint

A sample size of 450 will have > 99% power to detect a 0.75 g/dL difference in mean Hb values between the two treatment groups, assuming that the common standard deviation is 1.2 g/dL, using an analysis of variance (ANOVA) test with a 0.05 two-sided significance level.

For the comparisons of individual treatment arms for each of the 3 dose frequencies of roxadustat for Hb maintenance versus pooled placebo, a sample size of 35 roxadustat and 150 placebo will have 90% power to detect a 0.75 g/dL difference in mean Hb values between the

two treatment groups, assuming that the common standard deviation is 1.2 g/dL, using an ANOVA test with a 0.05 two-sided significance level.

For Ex-US Submission Primary Efficacy Endpoint

Based on a two-sided test at the $\alpha = 0.05$ level of significance, 450 subjects will have > 95% power to demonstrate a statistically significant difference between roxadustat and placebo, assuming that the proportion of subjects with a Hb response in the roxadustat group is at least 65% and the proportion of subjects with a Hb response in the placebo group is at most 25%.

During the course of this Phase 3 study, which is being conducted in parallel with other Phase 3 studies, up to 1200 subjects may be enrolled in this study to support the overall safety evaluation of roxadustat across pooled multiple studies in the Phase 3 program, including adjudicated composite safety endpoints of interest. The study will stop enrollment at the Sponsor's discretion if:

- 1) The minimum of 450 subjects has been achieved to support the primary endpoint in this individual study, and

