5.3 METHODOLOGY AND CONVENTIONS

Continuous variables will be presented by descriptive statistics: n, mean, standard deviation, median, minimum, and maximum. Categorical variables will be presented by frequency count and percentage.

Lab results obtained from the central laboratory, rather than local laboratories, will be used for all efficacy and safety analyses. Local laboratory values, if collected in the CRF's, will be listed.

The treatment groups will be presented as follows:

Roxadustat QW(1A), Roxadustat BIW(2A), Roxadustat TIW(3A), Pooled Roxadustat (1A+2A+3A), Pooled Placebo (1P+2P+3P). Most safety and efficacy tables will be presented by Pooled Roxadustat vs. Pooled Placebo. Selected safety and efficacy tables will present randomized treatment arms of QW, BIW and TIW if the patient received the actual maintenance dosing frequency for QW, BIW and TIW. In these tables, Roxadustat subjects who were randomized to BIW or QW under Amendment 1 but never switched (e.g., due to Amendment 2) to that maintenance frequency will not be presented in BIW or QW group, but in the TIW and pooled Roxadustat groups.

The statistical comparisons will be done between roxadustat against Placebo as deemed appropriate, where the groups before amendment 2 are pooled

Unless otherwise stated, all statistical tests will be two-sided hypothesis tests performed at the 5% level of significance for main effects and all confidence intervals will be two-sided 95% confidence intervals.

The primary and secondary endpoints will be tested sequentially using the fixed sequence approach for multiplicity adjustments at an alpha level of 0.05. There will be no adjustments for multiple comparisons for other tests.

All analyses will be performed using SAS[®] Version 9.1.3 or higher.

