12.2.1 Change in Hb - MMRM Model

As sensitivity analysis, a mixed model of repeated measures (MMRM) approach will be used. The model will contain terms for treatment arm, baseline Hb and eGFR measurements, visit, treatment*visit, and the other randomization stratification except baseline Hb (≤ 8 vs > 8) and eGFR as fixed effects. The primary efficacy analysis will be based on the estimated difference in the overall mean effect between the two treatment groups throughout the Evaluation Period based on the MMRM model.

The MMRM model will be used to compare the pooled roxadustat vs. pooled placebo. H_0 will be tested at the two-sided $\alpha = 0.05$ level of significance and will be rejected if the $p < 0.05$ from the test.

Due to the large amount of visits (up to week 52) to include in the model, the unstructured covariance pattern model will be applied first. If the algorithm for unstructured covariance pattern does not converge, then the heterogeneous Toeplitz structure will be used instead. If this second model also does not converge, then the (homogeneous) Toeplitz structure will be tried, and finally compound symmetry will be used as the covariance structure to achieve convergence. If none of them converge, first order autoregressive (AR (1)) as a covariance structure will be used to achieve convergence.

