10. Mean CFB in the SF-36 PF subscore averaged over Weeks 12 to 28 for the two treatment groups will be compared using an MMRM model as outlined above. A subgroup of subjects with baseline PF subscore below 50 will be analyzed as a sensitivity analysis.
11. Mean CFB in MAP averaged over Weeks 20 to 28 for the two treatment groups will be compared using an MMRM model as outlined above with a non-inferiority margin of 5.

12. Time to (and proportion of subjects with) protocol defined worsened hypertension for the pooled roxadustat vs pooled placebo will be compared using the approach in #4 above. Hazard ratio and its associated 95% CI will be computed between the roxadustat group versus pooled placebo. Non-inferiority will be declared if the upper bound of the 2-sided 95% CIs of the odds ratio does not exceed 1.3. Superiority will be declared if the upper bound of the 2-sided 95% CI of the hazard ratio does not exceed one. The incidence rate per PEY by treatment group will also be reported.

In MMRM above, due to large amount of visits to include in the model, the unstructured covariance pattern model will be applied first. If the algorithm for unstructured covariance pattern does not converge, then the heterogeneous Toeplitz structure will be used instead. If this second model also does not converge, then the (homogeneous) Toeplitz structure will be tried, and finally compound symmetry as a covariance structure to achieve convergence. If none of them converge, first order autoregressive (AR (1)) as a covariance structure will be used to achieve convergence.

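### The MMRM covariance fallback is chosen by convergence alone and no standard-error method is stated; compound symmetry with model-based errors could push the Hb, MAP and LDL tests above their nominal error rate

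*SAP*

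**What the plan says.** SAP 12.3 sets one covariance strategy for all its MMRM analyses: unstructured, heterogeneous Toeplitz, homogeneous Toeplitz, "and finally compound symmetry as a covariance structure to achieve convergence", and AR(1) if none of these converges. SAP 12.2.1 gives the same order for the MMRM sensitivity analysis of the US primary endpoint ("finally compound symmetry will be used as the covariance structure to achieve convergence", again followed by AR(1)). Protocol 9.4.3.2 has the same list without AR(1). All three sections give the number of visits as the reason for the list. Convergence is the only criterion for moving down it.

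No section names model-based, empirical or Kenward-Roger standard errors, or a degrees-of-freedom method, for these models.

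The tests carry controlled alpha. SAP 5.3 states that "all statistical tests will be two-sided hypothesis tests performed at the 5% level of significance for main effects" and that "The primary and secondary endpoints will be tested sequentially using the fixed sequence approach for multiplicity adjustments at an alpha level of 0.05". In the SAP 12.3 sequence, Hb Weeks 28-36 is item 1 (Ex-US only), LDL is item 5 and MAP, with a non-inferiority margin of 5, is item 11.

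**The concern.** A structure that converges need not be right. With an unstructured covariance, model-based errors are sound. With a simplified structure they are sound only if that structure is close to the truth.

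Compound symmetry gives every pair of visits the same correlation, estimated as an average over all visits to Week 52. Each endpoint here is an average over a few neighbouring visits. If correlation falls with time, those visits are more alike than the all-visit average, so the variance of their mean is understated. The Toeplitz steps are also approximations: they treat adjacent visits alike although the gaps are 1, 2 and 4 weeks.

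An interval that is too narrow makes both superiority and non-inferiority easier to declare, and in a fixed sequence a false rejection opens the next test. MAP is the most exposed, because the error there favours a conclusion of no blood-pressure harm.

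**Working it through.** **1. The plan's own figures.** Power = Φ(δ / [σ√(1/n₁ + 1/n₂)] − 1.96).
- SAP 5.1: "A sample size of 450 will have > 99% power to detect a 0.75 g/dL difference in mean Hb values", "assuming that the common standard deviation is 1.2 g/dL", allocation "2:1 with approximately a minimum of 300 roxadustat vs 150 placebo". SE = 1.2√(1/300 + 1/150) = 0.120; 0.75/0.120 = 6.25; power = Φ(4.29), above 99.99%. Agrees.
- SAP 5.1: "a sample size of 35 roxadustat and 150 placebo will have 90% power to detect a 0.75 g/dL difference in mean Hb values between the" arms. SE = 1.2√(1/35 + 1/150) = 0.225; 0.75/0.225 = 3.33; power = Φ(1.37) = 91.5%. Close to the stated figure.

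These figures contain no within-subject correlation, so every correlation below is an assumption.

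**2. Size of the models.** Hb and blood-pressure visits (Protocol 4.5.1 and Appendix 2): Weeks 1 and 2, 4 to 24 by 2 (11 visits), 28 to 52 by 4 (7 visits), 20 in all. Unstructured needs 20 × 21/2 = 210 parameters, homogeneous Toeplitz 20, compound symmetry 2. Lipids to Week 52 (Weeks 4, 8, 12, 20, 28, 36, 44, 52): 8 × 9/2 = 36. SF-36 (SAP Table 17.1-2, Weeks 12, 28, 52): 3 × 4/2 = 6.

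**3. Formula.** For k visits with equal variance and average pairwise correlation r, the variance of their mean is proportional to [1 + (k − 1)r]/k. With complete data, compound symmetry uses the all-visit average r_all; the truth is the window average r_win.
- SE ratio q = √{[1 + (k − 1)r_all] / [1 + (k − 1)r_win]}
- Two-sided type I error = 2[1 − Φ(1.96q)]; the one-directional rate is half of that, against 2.5%.

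Assumed correlation at a gap of d weeks: f + (1 − f)ρ^(d/4), with ρ = 0.7-0.9 and floor f = 0-0.4.

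**4. Worked case, ρ = 0.8, f = 0.**
- Hb (Weeks 28, 32, 36): r_all = 0.443; r_win = (0.8 + 0.8 + 0.64)/3 = 0.747. Variances (1 + 2 × 0.443)/3 = 0.629 and (1 + 2 × 0.747)/3 = 0.831. q = 0.870; error 8.8%.
- MAP (Weeks 20, 22, 24, 28): r_all = 0.443, r_win = 0.791. Variances 0.582 and 0.843. q = 0.831; error 10.3%.
- LDL (Weeks 12, 20, 28): r_all = 0.378, r_win = 0.563. Variances 0.586 and 0.709. q = 0.909; error 7.5%.

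Simulation of this case (8,000 trials, 300 vs 150, complete data) gave 8.4%, 10.2% and 7.1%.

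**5. Whole assumed range.**

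| Endpoint | SE ratio | Two-sided error | One-directional rate |
|---|---|---|---|
| Hb Weeks 28-36 | 0.85-0.95 | 6.2-9.6% | 3.1-4.8% |
| MAP Weeks 20-28 | 0.80-0.94 | 6.5-11.9% | 3.3-6.0% |
| LDL Weeks 12-28 | 0.91-0.96 | 5.9-7.5% | 2.9-3.8% |

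**6. Other assumed patterns (two-sided, compound symmetry, model-based errors).**
- Compound symmetry true: 5.0%.
- LDL SD rising 1.3- to 1.5-fold by Week 52, after the window: 3.4-3.7%, so intervals are too wide.
- Dropout of 30% vs 50% by Week 52, completely at random: Hb 6.0-12.0%, MAP 6.2-12.6%, LDL 5.1-6.9%.
- SD rising over the first 24 weeks from 50-70% of its later value: Hb 9-17%, MAP 9-15%, LDL 6-9%.

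**7. Remedies.** Sandwich errors on the same compound-symmetry fit gave simulated error of 4.7-5.4% in every complete-data scenario. AR(1) with model-based errors gave 4.0-7.1% with equal variances, and about 8-11% for Hb and MAP when the SD rises early.

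**The case against.** A prespecified list that starts from unstructured is a defensible plan, and the trigger is remote. Homogeneous Toeplitz needs only 20 parameters for Hb, on up to 450 × 20 = 9,000 observations. In 15 simulated data sets (300 vs 150, assumed 30%/50% dropout, 5% intermittent missingness) the unstructured Hb covariance converged every time. That was a small check, and it used an EM algorithm rather than the SAS one. LDL, with 36 parameters, is less likely still to fall back. For Hb the planned effect gives an expected z of 6.25, so a 10-15% error in the standard error would not change the conclusion. All of this stands. It limits the likelihood and, for Hb, the consequence; it does not supply the missing standard-error rule.

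Several stronger readings are tempting and not supported:
- **That the plan chose model-based errors.** The documents are silent; inflation follows only if a model-based default is used.
- **That the SAP list ends in compound symmetry.** Only the protocol's does. In the SAP it is the practical end, because a two-parameter model rarely fails.
- **That the intervals will be too narrow.** Under some variance patterns they are correct or too wide.
- **That the two-sided MAP figure is the false non-inferiority rate.** That rate is half of it.
- **That SF-36 is at similar risk.** Three visits and 6 parameters make a fallback unlikely.
- **That the US primary result is exposed.** It uses MI ANCOVA; only its MMRM sensitivity analysis shares the list.

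**Conclusion.** The gap is real but conditional. If a structured fallback is reached, nothing in either document protects the intervals and p-values against a wrong structure. For compound symmetry with model-based errors, correlation decaying as assumed and equal variances, two-sided type I error is about 6-10% for Hb, 6.5-12% for MAP and 6-7.5% for LDL. The corresponding one-directional false-claim rates are about 3-6% against 2.5%, with MAP non-inferiority the case to worry about.

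These sizes rest on correlations the documents do not give, and the error can be at or below nominal. The probability of reaching the fallback is unknown and probably low. The point is worth acting on because the remedy is cheap and must be prespecified.

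**What to change.** Add to SAP 12.2.1 and 12.3: if any covariance structure other than unstructured is used, standard errors, confidence intervals and p-values come from the empirical (sandwich) estimator clustered on subject; the unstructured fit uses Kenward-Roger inference. Align the lists in Protocol 9.4.3.2 and the SAP, which differ on AR(1). Swapping AR(1) and compound symmetry is not a substitute, since model-based AR(1) also misses the nominal rate and ignores the unequal visit spacing.

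The cost is one sentence and one procedure option. Sandwich errors are slightly less stable in small samples, a small loss with at least 450 randomized subjects; the set for MAP will be smaller, because SAP 12.3 tests non-inferiority in the per-protocol set. They correct the error bars only. If dropout depends on earlier outcomes, a misspecified covariance can bias the estimate itself, and SAP 13.1.2 already suspects differential dropout. Unstructured should therefore remain the first choice, and the report should state which structure was used.
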